### 10.4 Sample size justification

The sample in each cohort is based on having 80% power to detect an average increase in CAV1 staining of 20% using a one-sided Wilcoxon signed-rank test with  $\alpha=0.05$ . Based on pilot data in other cancers, we assume the standard deviation of change scores to be 32%. A sample size of 19 per cohort is required under these assumptions. Allowing for approximately 15% of patients to have missing pre- and or post-treatment data, we will recruit 23 women per cohort. Cohort 1 will consist of breast cancer patients and cohort 2 will include both uterine and cervical (gynecologic) cancers.

### 10.5 Interim analysis and early stopping.

There will be no interim analysis for efficacy or futility.

### 10.6 Stopping rules for safety

Incidence of DLTs will be monitored continuously with potential stopping after 10 patients have been enrolled based on the Bayesian method of Thall and Simon. We are comparing our experimental treatment to a standard of no treatment and assume no DLTs under standard of care. Both agents are extremely safe and DLTs should be exceedingly rare. In 900 patients treated with metformin alone, the discontinuation rate was 0.6%. In 31 patients treated with IV doxycycline, 4 SAEs were observed, but none were related to the study drug. Thus, it is reasonable to assume a prior distribution for the DLT rate in the combination of  $\text{Beta}(0.04, 1.96)$ .

That is, we assume a 2% event rate for the combination with information equivalent to data from 2 patients. We will stop the study for safety if the posterior probability that the rate of DLTs in the combination treatment is 5% or greater is greater than 90%. Stopping rules are outlined in the table below.

Number of patients enrolled	Stop if number of patients with Grade 3 or higher toxicities is $\geq$
10	2
11-22	3
23-35	4
36	5

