## Required Enrollment

23 patients per cohort (breast and uterine/cervical) for a total of 46 patients

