**Statistical Analysis:**

The primary objective of the study is to assess the impact of metformin and doxycycline on the percent of stromal cell that have CAV1 expression by immunohistochemistry (IHC) in carcinoma cells. All patients from whom samples are obtained both pre- and post-treatment will be included in the primary analyses. Within-patient change in IHC scores will be analyzed using the Wilcoxon signed-rank test.

The sample in each cohort is based on having 80% power to detect an average increase in CAV1 staining of 20% using a one-sided Wilcoxon signed-rank test with  $\alpha=0.05$ . Based on pilot data in other cancers, we assume the standard deviation of change scores to be 32%. A sample size of 19 per cohort is required under these assumptions. Allowing for approximately 15% of patients to have missing pre- and or post-treatment data, we will recruit 23 women per cohort.

Incidence of Dose Limiting Toxicities (DLTs) will be monitored continuously with potential stopping after 10 patients have been enrolled based on the Bayesian method of Thall and Simon. We are comparing our experimental treatment to a standard of no treatment and assume no DLTs under standard of care. Both agents are extremely safe and DLTs should be exceedingly rare. In 900 patients treated with metformin alone, the discontinuation rate was 0.6%. In 31 patients treated with IV doxycycline, 4 SAEs were observed, but none were related to the study drug. Thus, it is reasonable to assume a prior distribution for the DLT rate in the combination of Beta (0.04,1.96). That is, we assume a 2% event rate for the combination with information equivalent to data from 2 patients. We will stop the study for safety if the posterior probability that the rate of DLTs in the combination treatment is 5% or greater is greater than 90%.

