#### 4.4 Recruitment and Screening

46 subjects will be recruited. No advertisement will be conducted. Screening requirements include serum measurement of creatinine, aspartate aminotransferase, alanine aminotransferase and alkaline phosphatase taken on a non-fasting blood sample. Potential research subjects will be identified by a member of the patient's treatment team, the protocol investigator, or research team at participating centers from Medical Oncology, Radiation Oncology and Surgical offices. Investigators will screen the patient's medical records for suitable research study subjects and discuss the study and their potential for enrolling in the

research study. Patients will be screened based on pathology, image studies etc. A maximum of 23 patients will be enrolled onto each arm of the trial (see Statistical Analysis Plan Section 9).

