## 10 Statistical Analysis Plan

### 10.1 General considerations:

All analyses will be performed separately by cohort.

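### The Section 10.6 stopping table ends at patient 36 of 46, and the Bayesian rule waits for patient 10 even after two DLTs have settled the decision

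*Combined protocol and SAP*

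**What the plan says.** Section 10.6 sets a Bayesian safety rule. On the prior, the Study Summary (Statistical Analysis) says "it is reasonable to assume a prior distribution for the DLT rate in the combination of Beta (0.04,1.96"), which is a 2% mean rate carrying the weight of two patients; Section 10.6 repeats it. The criterion is: "We will stop the study for safety if the posterior probability that the rate of DLTs in the combination treatment is 5% or greater is" above 90%. On timing: "Incidence of DLTs will be monitored continuously with potential stopping after 10 patients have been enrolled".

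The accompanying table has two columns, headed "Number of patients enrolled" and "Stop if number of patients with Grade 3 or higher toxicities is" at or above a given count. Its rows are 10 (boundary 2), 11–22 (3), 23–35 (4) and 36 (5). Nothing is printed for 1–9 or 37–46.

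The planned size is "23 patients per cohort (breast and uterine/cervical) for a total of 46 patients"; Section 4.4 agrees ("46 subjects will be recruited"). Section 10.1 says "All analyses will be performed separately by cohort". Sections 8.5 and 13.7 separately allow the study to be terminated on safety grounds by judgement, with no minimum enrolment and no posterior or count threshold of this kind.

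**The concern.** A monitoring committee works from the table. For the last 10 of 46 patients the table gives no number, although monitoring is described as continuous and the two rows before the last are ranges.

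At the other end, the rule is silent until 10 patients are enrolled, yet the boundary at 10 is only two events. A DLT count cannot go down. Once two DLTs have occurred among fewer than 10 patients, the stop at 10 is fixed, and any patient enrolled in the meantime is exposed without being able to affect the decision. At stake are a small number of avoidable exposures, and some lost chance of stopping late if the table is read literally.

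**Working it through.** **Inputs.** Prior Beta(0.04, 1.96), limit 5%, threshold 90%, first action at 10 patients, and the printed rows (all Section 10.6); 46 patients (Required Enrollment; Section 4.4). Assumptions: both cohorts are pooled, DLTs are known at once, and the DLTs are the Grade 3 or higher events that the table counts.

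**Formula.** With x events in n patients the DLT rate has posterior Beta(0.04 + x, 1.96 + n − x). The boundary at n is the smallest x for which Pr(rate ≥ 0.05) > 0.90.

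**Step 1: reproduce the printed table.** Posterior probabilities at the change points:

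| n | x | Pr(rate ≥ 5%) | Consequence |
|---|---|---|---|
| 10 | 2 | 0.9048 | boundary 2 |
| 11 | 2 | 0.8890 | boundary rises to 3 |
| 22 | 3 | 0.90005 | boundary 3 |
| 23 | 3 | 0.8896 | boundary rises to 4 |
| 35 | 4 | 0.9006 | boundary 4 |
| 36 | 4 | 0.8927 | boundary rises to 5 |
| 36 | 5 | 0.9658 | boundary 5 |

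Every printed row is correct.

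**Step 2: extend to 46.** At n = 46, x = 5 gives 0.9188 and x = 4 gives 0.7992. The posterior for a fixed x falls as n rises, so the boundary is 5 for all of 36–46. It would stay at 5 up to n = 49 (0.9002) and rise at n = 50 (0.8935).

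**Step 3: two DLTs before patient 10.** With x = 2:

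| n | 2 | 3 | 4 | 5 | 6 | 7 | 8 | 9 |
|---|---|---|---|---|---|---|---|---|
| Posterior | 0.9937 | 0.9876 | 0.9797 | 0.9702 | 0.9594 | 0.9473 | 0.9341 | 0.9199 |

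The criterion is met at every one of these n. It is still met at n = 10 with no further DLT (0.9048), so the stop at 10 is certain.

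**Step 4: one early DLT.** With x = 1 the posterior is 0.9136 at n = 1 and 0.8710 at n = 2. A single DLT therefore meets the criterion only if it occurs in patient 1.

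**Step 5: operating characteristics**, by exact patient-by-patient recursion to n = 46. A: looks at 10–36 only. B: looks at 10–46. C: as B, plus a boundary of 2 at n = 2–9. Each cell gives the probability of stopping and the mean enrolment.

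| True rate | A | B | C | B − C (patients) | P(≥2 DLTs in first 9) |
|---|---|---|---|---|---|
| 2% | 2.3%; 45.25 | 2.4%; 45.25 | 2.4%; 45.20 | 0.04 | 1.3% |
| 5% | 16.8%; 41.07 | 18.3%; 41.03 | 18.3%; 40.78 | 0.25 | 7.1% |
| 10% | 55.6%; 29.91 | 61.9%; 29.70 | 61.9%; 28.85 | 0.85 | 22.5% |
| 15% | 83.5%; 20.54 | 89.2%; 20.34 | 89.2%; 18.73 | 1.61 | 40.1% |
| 20% | 95.4%; 15.13 | 97.9%; 15.03 | 97.9%; 12.61 | 2.42 | 56.4% |

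(Differences are taken before rounding.) B and C have the same probability of stopping because every path that C stops before 10 is stopped by B at 10.

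If the posterior rule is instead applied from patient 1, so that one DLT in patient 1 stops the study, the probability of stopping at a true 2% rate rises from 2.4% to 4.0%.

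**The case against.** Four points on the other side carry weight.

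- **The written criterion covers the whole trial.** A reader might infer that the last 10 patients have no safety rule. The documents do not support that: the prior and the criterion are given in words, monitoring is continuous, and together they fix the boundary at 5 for 37–46. The lone 36 may well have been meant as 36 or more. The drop from B to A is a loss only if the criterion is ignored after patient 36, and even then mean enrolment differs by only about 0.2 patients at 10% and 15%.
- **The study can be stopped before patient 10.** A reader might infer a general bar. Only the Bayesian rule waits; Sections 8.5 and 13.7 permit termination at any enrolment. Those clauses rest on judgement, though, and set no numerical trigger equivalent to the rule.
- **The minimum has a purpose.** A reader might conclude that it should be removed. Step 4 shows why not: it prevents a stop driven by a weak prior and one event in patient 1. That argument protects against one early DLT; it gives no reason to wait after two.
- **The early cost is small near the planned rate.** It is 0.04 patients at 2%. The conditional figure is larger (2.42 / 0.564 = 4.3 further patients at 20%, given two DLTs in nine), but 20% is ten times the prior mean. Delayed ascertainment would also shrink the saving.

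Indexing rows by patients enrolled, when DLTs count until 30 days after therapy (Section 5.2.5), is a minor matter. At 46 patients in 36 months (1.28 a month) and a window of 37 to 65 days (7 to 35 days of dosing plus 30), about 1.6 to 2.7 patients are inside the window at a time. Pooling is likewise already implied, because the rule stops the study and its rows run past the 23-patient cohort cap.

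**Conclusion.** The point holds in a limited form. The printed boundaries are right. The table is incomplete for 37–46, where the stated criterion supplies the missing value of 5. The wait until patient 10 serves no purpose once two DLTs have occurred. Acting on the second DLT at once leaves the probability of stopping unchanged at every true rate, and it cuts mean enrolment by 0.04, 0.25, 0.85 and 2.4 patients at 2%, 5%, 10% and 20%.

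This rests on the look at exactly 10 patients being made (at 11 the boundary is 3), on pooled monitoring, on immediate ascertainment, and on the DLTs being the Grade 3 or higher events in the table. Section 5.2.5 gives no grade threshold for a DLT, so the last assumption is not secured by the text. A per-cohort reading under Section 10.1 would remove the 37–46 gap, since no cohort exceeds 23, but it would leave the rows above 23 without use.

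**What to change.** In Section 10.6:

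- **(a)** Relabel the last row 36–46, boundary 5. If replacements under Section 4.5.1 could take enrolment past 46, note that 5 remains the boundary up to 49.
- **(b)** Change the first row to 2–10, boundary 2, and state that before patient 10 the Bayesian rule acts only on two or more DLTs. This sentence must accompany the row, so that the raw posterior cannot stop the study on one DLT in patient 1.
- **(c)** As a minor clarification, state that the safety rule pools both cohorts, as an exception to Section 10.1.

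The cost is two row labels and two sentences. The prior, the 5% limit and the 90% threshold stay, and the probability of stopping at a true 2% rate stays at 2.4%. Deleting the minimum outright is not an equivalent edit, because it would raise that figure to 4.0%.

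### Section 10.6 has no formal DLT stop before 10 patients, although two DLTs meet the plan's own criterion at every enrolment from 2 to 10

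*Combined protocol and SAP*

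**What the plan says.** Section 10.6 states: "Incidence of DLTs will be monitored continuously with potential stopping after 10 patients have been enrolled". The Statistical Analysis part of the Study Summary repeats that DLTs "will be monitored continuously with potential stopping after 10 patients have been enrolled". The prior for the DLT rate is Beta(0.04, 1.96), which the plan explains as "we assume a 2% event rate for the combination with information equivalent to data from 2 patients". The criterion is: "We will stop the study for safety if the posterior probability that the rate of DLTs in the combination treatment is 5% or greater" exceeds 90%.

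The table in 10.6 sets limits of 2 at 10 patients, 3 at 11-22, 4 at 23-35 and 5 at 36. It has no row below 10, and the documents give no reason for starting there. The column heading begins "Stop if number of patients with Grade 3 or higher toxicities is", whereas the text of 10.6 speaks of DLTs.

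Two other routes to stopping have no minimum enrolment. Section 8.5 says the study may be terminated for toxicity of grade 4 or above at the lowest dose. Section 13.7 has the medical monitor review SAEs as they are reported.

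**The concern.** A minimum sample before formal monitoring normally guards against stopping on a chance cluster among the first few patients. That works when the later boundary needs more events than the early cluster supplies. Here the limit at 10 patients is 2, the same number that satisfies the criterion at any enrolment from 2 upwards. Once two DLTs are on record, the next patients cannot bring the count back below the limit.

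At stake is the exposure of patients enrolled between the second DLT and patient 10. Section 1.4.1 says that significant clinical benefit to participants is unlikely, so exposure that does not inform the safety decision is hard to justify.

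**Working it through.** **Inputs.** From 10.6: prior Beta(0.04, 1.96), DLT threshold 5%, posterior cut-off 90%, and the boundary table. From Required Enrollment: "23 patients per cohort (breast and uterine/cervical) for a total of 46 patients". Two readings are assumed: the table pools the cohorts (its rows run past 23), and the last row, printed as 36, covers 36-46.

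**Step 1: reproduce the plan's table.** With x DLTs in n patients the posterior is Beta(0.04 + x, 1.96 + n − x). The limit is the smallest x for which P(rate ≥ 5%) > 0.90. This gives 2 at n = 10, 3 at 11-22, 4 at 23-35 and 5 at 36-46. It matches the plan at every n from 10 to 46.

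**Step 2: apply the same criterion below 10.** With x = 2:

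| n | 2 | 3 | 4 | 5 | 6 | 7 | 8 | 9 | 10 |
|---|---|---|---|---|---|---|---|---|---|
| P(rate ≥ 5%) | 0.994 | 0.988 | 0.980 | 0.970 | 0.959 | 0.947 | 0.934 | 0.920 | 0.905 |

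All exceed 0.90. With x = 1 the posterior is 0.914 at n = 1 and 0.871 at n = 2, and it falls further after that. So one DLT meets the criterion only if it occurs in the very first patient.

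**Step 3: effect of starting at 2.** The comparison uses an exact forward recursion over n = 1 to 46 and assumes each DLT is known before the next enrolment. Under either start, the trial stops by patient 10 exactly when at least 2 of the first 10 patients have a DLT. At a 20% rate, for example, this probability is 1 − 0.8^10 − 10 × 0.2 × 0.8^9 = 0.624. Beyond patient 10 the rules are the same, so the overall stopping probability cannot differ.

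| True DLT rate | P(stop), either start | Expected enrolment, start at 10 | Expected enrolment, start at 2 | Saving | P(second DLT before patient 10) |
|---|---|---|---|---|---|
| 2% | 2.4% | 45.25 | 45.20 | 0.04 | 1.3% |
| 5% | 18.3% | 41.0 | 40.8 | 0.25 | 7.1% |
| 10% | 61.9% | 29.7 | 28.9 | 0.85 | 22.5% |
| 20% | 97.9% | 15.0 | 12.6 | 2.4 | 56.4% |
| 30% | 99.97% | 11.2 | 7.2 | 3.9 | 80.4% |

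**Step 4: patients enrolled after the second DLT.** Dividing the saving by the last column gives the mean number enrolled up to patient 10 when the second DLT comes before patient 10. It is 3.4 at 2%, 3.5 at 5%, 0.848/0.2252 = 3.8 at 10%, 4.3 at 20% and 4.9 at 30%. The maximum is 10 − 2 = 8. It needs DLTs in both of the first two patients, which has probability 0.04% at a 2% rate, 0.25% at 5% and 4% at 20%.

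**Step 5: recognition lag.** Dosing of 7-35 days plus 30 days (5.2.5) gives a DLT window of 37-65 days. At an assumed even accrual of 46 in 36 months (about 1.3 per month), roughly 1.6 to 2.7 patients enrol within one window. If the second DLT is recognised only after patient 11 has enrolled, the limit is already 3, and two DLTs (posterior 0.889) no longer trigger the rule.

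**The case against.** A reader might infer that the plan forbids stopping before patient 10. It does not. Sections 8.5 and 13.7 allow termination at any enrolment. Section 8.4.2 also sends related grade 4-5 events, and related grade 3 events with hospitalization, to the DSMC within 48 hours. These routes narrow the gap but do not close it. They are discretionary or concern reporting only, and none sets a number for two grade 3 events. Under 8.4.2 an expected, related grade 3 event without hospitalization waits for the quarterly DSMC meeting.

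A reader might also infer that eight patients would typically be treated to no purpose. Eight is the extreme case, and the average saving is below one patient at true rates up to 10%. The later patients add nothing to the DLT decision, but they still supply paired CAV1 samples for the primary analysis.

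Nor is the stop at patient 10 unconditionally certain. Relatedness can be reassessed, recognition can lag, and 4.5.1 replaces discontinued patients without saying whether their DLTs stay in the count.

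Finally, the start at 10 is a stated design choice, and error control is the same either way. That limits the weight of the point. It does not supply a reason for the delay, because the only early stop that a later start usefully avoids is one DLT in the first patient, and a start at 2 avoids that too.

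**Conclusion.** The point holds in limited form: 10.6 provides no formal stop before 10 patients, although its own criterion is met by two DLTs at every enrolment from 2 to 10. The delay lowers no false-stop risk. The gain from closing the gap is small if the assumed 2% rate is about right and reaches 2.4 to 3.9 patients at true rates of 20-30%, which is where a safety rule matters. The unchanged stopping probability and the enrolment figures assume that each DLT is known before the next enrolment, that DLTs remain counted, that the cohorts are pooled and that the last row runs to 46. This is a free improvement of modest size, not a failure of the safety monitoring.

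**What to change.** Add a first row to the table in 10.6: **2-9 patients, stop if 2 or more**. Leave the other rows unchanged. In 10.6 and in the Study Summary, change the enrolment at which stopping becomes possible from 10 patients to 2. Do not simply delete the phrase. Without a stated start, the text criterion would be met by one DLT in the first patient (0.914), which would contradict a table that begins at 2.

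Reconcile the counted event as well. The text counts DLTs, which 5.2.5 requires to be related to study therapy, while the table heading counts grade 3 or higher toxicities. State which event applies, and whether DLTs in patients replaced under 4.5.1 stay in the count.

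The cost is one table row, one changed number in two places and a clarified heading. On the assumptions above, no extra patients are needed and the chance of stopping is unchanged at any true DLT rate.

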### **5.2.5 Dose Limiting Toxicity Criteria**

Dose-limiting toxicities (DLTs) will be graded in severity according to the guidelines outlined in the NCI- CTCAE version 4.03. Dose-limiting hematologic and non-hematologic toxicities will be defined differently, and will be based on events that occur during study drug administration and for 30 days after the completion of the therapy. In order to be declared a dose-limiting toxicity, an adverse experience must be related (definitely, probably, or possibly) to study therapy.

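### The safety boundary in 10.6 is built for dose-limiting toxicities, but its table counts Grade 3 or higher toxicities and no DLT criteria are supplied, so the rule can be run on two different events

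*Combined protocol and SAP*

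**What the plan says.** Section 10.6 (Stopping rules for safety) defines the rule on DLTs: "Incidence of DLTs will be monitored continuously with potential stopping after 10 patients have been enrolled". Its prior is Beta(0.04, 1.96), explained as "we assume a 2% event rate for the combination with information equivalent to data from 2 patients". The study stops when the "posterior probability that the rate of DLTs in the combination treatment is 5% or greater is greater than 90" per cent. No DLTs are assumed under standard care. The Study Summary repeats all of this.

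The table that puts the rule into practice has the column heading "Stop if number of patients with Grade 3 or higher toxicities is", with limits of 2 at 10 patients, 3 at 11–22, 4 at 23–35 and 5 at 36. It mentions neither DLTs, nor relation to treatment, nor a time window, nor a data source.

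Section 5.2.5 (Dose Limiting Toxicity Criteria) sets the attribution: "In order to be declared a dose-limiting toxicity, an adverse experience must be related (definitely, probably, or possibly) to study therapy". The window is the treatment period plus 30 days. On content it says "Dose-limiting hematologic and non-hematologic toxicities will be defined differently", but no grade or list of events follows there or elsewhere.

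Section 5.3 (Surgical Resection) sends adverse events that the investigator considers related to surgery to source documents and keeps them off the CRFs.

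**The concern.** A stopping boundary is valid only for the event whose rate it was derived for. Here the derivation concerns drug-related DLTs, expected in about 2% of patients, and the table that monitors would use names a different event. The text version cannot be applied as written, because no criteria say which related events are DLTs. The table version can be applied, but not necessarily to DLTs.

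The two counts can differ in both directions. An unrelated Grade 3+ event fits the table heading but is not a DLT. A related event below Grade 3 could be a DLT, since no grade is set, but would not enter the table. Two monitors with the same patients could therefore disagree on whether the study must stop, and at 10 patients the decision turns on only two of them. This is the only quantitative safety stopping rule in the plan.

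**Working it through.** **Inputs from the documents.** Prior Beta(0.04, 1.96), limit 5%, criterion 90%, first look at 10 patients (10.6); maximum enrolment 46, as 2 × 23 (Study Summary). **Assumed.** The last table row, printed as 36, is read as 36–46. The rate of Grade 3+ events unrelated to the drugs is not given in the documents and is varied over a range.

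**Step 1: reproduce the table.** With x events in n patients the posterior is Beta(0.04 + x, 1.96 + n − x). The limit at n is the smallest x with P(rate ≥ 0.05) > 0.90. At the edges of the rows:

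| n | x | Posterior probability | Stop? |
|---|---|---|---|
| 10 | 2 | 0.905 | yes |
| 11 | 2 | 0.889 | no, 3 needed |
| 22 | 3 | 0.90005 | yes |
| 23 | 3 | 0.890 | no, 4 needed |
| 35 | 4 | 0.901 | yes |
| 36 | 4 | 0.893 | no, 5 needed |

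The computed limit equals the printed one at every n from 10 to 46. The printed numbers are thus the DLT boundary; only the column heading departs from the derivation.

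**Step 2: probability of stopping.** For a per-patient probability p of the counted event, an exact binomial recursion adds one patient at a time. From patient 10 it removes the probability at or above the limit; the sum removed by patient 46 is the probability of stopping. A check on the first look, by hand: P(X ≥ 2) = 1 − (1 − p)^10 − 10p(1 − p)^9, which is 0.016 at p = 0.02 and 0.264 at p = 0.10.

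| Rate of counted event | P(stop by 46) |
|---|---|
| 0.6% | 0.002 |
| 2% (planned DLT rate) | 0.024 |
| 5% | 0.183 |
| 10% | 0.619 |
| 15% | 0.892 |

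If the table is counted without regard to attribution and there are no DLTs at all, the 5%, 10% and 15% rows apply directly to the assumed unrelated rate. If the recursion is ended at patient 36 instead, the values at 2%, 5%, 10% and 15% are 0.02, 0.17, 0.56 and 0.84, so the reading of the last row matters little.

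**Step 3: planned DLT rate plus unrelated events.** Assuming independence, p = 1 − (1 − 0.02)(1 − q), where q is the assumed unrelated rate. For q = 5%, p = 1 − 0.98 × 0.95 = 0.069 and P(stop) = 0.346. For q = 10%, p = 1 − 0.98 × 0.90 = 0.118 and P(stop) = 0.745.

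**Step 4: the opposite error.** No figure can be given for DLTs that the table would miss, because 5.2.5 sets no grade and the documents give no rate for related events below Grade 3.

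**The case against.** A reader might infer that complications of surgery will trip the boundary and close a safe study. The documents do not support that.

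- Section 5.3 keeps events the investigator attributes to surgery off the CRFs, and 11.3 makes the CRF the primary data collection instrument. A count taken from CRFs would leave those events out.
- The table directly follows the DLT criterion in 10.6 and is introduced as setting out that rule. Its heading may be loose shorthand for DLT.
- Toxicity often means a drug effect in this protocol, as in the account of metformin's risks in 1.4.2.
- No peri-operative Grade 3+ rate is given, so the larger stopping probabilities are scenarios. They also need every such event to be counted.

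These points rule out a prediction of false stopping, but they do not settle what is counted. The table names no data source, and 8.4.2 sends all adverse events to the monitoring committee, with reporting rows for unrelated ones. Usage of toxicity is mixed: 5.2.1 adds drug-relatedness where it is meant, and 7.2.1 lists causality as a separate attribute of a toxicity. An event possibly related to both drug and surgery qualifies on attribution under 5.2.5, yet may be kept off the CRF under 5.3. Even if the heading is shorthand for DLT, the DLT criteria are still missing.

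**Conclusion.** The point holds as a mismatch between the event the boundary was derived for and the event its table counts, together with a DLT definition that is announced and not supplied. That part rests on the text and on exact reproduction of the table, and needs no assumption about event rates beyond those in the plan.

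The size of the consequence is conditional. The rule stops with probability 0.02 at the planned 2% rate, and 0.18, 0.62 or 0.89 if the counted event occurs in 5%, 10% or 15% of patients. These rates are assumptions, and the figures take the last row as 36–46. They show how far the result depends on what is counted; they are not an estimate of the false-stop risk, which 5.3 makes smaller by an unknown amount. The error can also run towards failing to stop, by an amount that cannot be computed from the documents.

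It should be corrected before the rule is used, because the rule decides whether the study continues.

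**What to change.** 1. In 10.6, change the column heading to the number of patients with a DLT, and print the last row as 36–46 if that is what is meant. The limits do not change, provided the sponsor still considers the 2% prior mean and 5% limit right for the DLT as defined.
2. In 5.2.5, have the sponsor supply the haematologic and non-haematologic criteria that the section announces. The choice of grade is the sponsor's.
3. Reconcile 5.2.5, 5.3 and 10.6 on grade, attribution, window and data source. State how surgery-related events are counted, including those possibly related to both drug and surgery.
4. In 8.5, add a sentence saying how its separate, discretionary halting rule relates to 10.6, leaving that rule's own threshold as it is.

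The cost is an amendment to protocol and SAP wording. Sample size and boundary numbers are unaffected. If surgery-related events of mixed attribution are to be counted, the CRF must be able to record them.
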